8.3. Survey design

8.3.1. Survey Instruments

There are two survey instruments included in this study, (1) a HCP survey and (2) a parent/carer survey.

Following agreement to participate, the understanding of the potential risks associated with Strimvelis will be evaluated via telephone interview. The telephone interviews will be conducted in the local countries language. The survey will start with screening questions to ensure eligibility and willingness to participate in the survey. Participation in the study can be terminated during screening. The survey will include multiple choice and close-ended questions. There will be no open-ended questions included.

Survey questions are based on the Strimvelis prescribing information and educational materials including those that address risks of autoimmunity, unsuccessful response, oncogenesis and pregnancy. There will be approximately 20 questions per survey.

For HCPs, the survey refers to the following risk minimisation measures:

- Educational materials:
 - Important risk minimisation information for healthcare professionals who provide long-term follow-up of ADA-SCID patients post-treatment with Strimvelis
- Strimvelis Summary of Product Characteristics

For parents/carers, the survey refers to the following risk minimisation measures:

- Educational materials:
 - "Important follow-up risk minimisation information for children who have received gene therapy with Strimvelis (autologous CD34+ cells transduced to express ADA) an educational leaflet for parents/carers"
 - Patient Treatment Alert Card
- Strimvelis Patient Information Leaflet

The questions will evaluate HCPs' and patients'/carers' understanding of the key risk messages (KRMs) of the routine and additional risk minimisation measures. The questions will also assess HCPs' and patients'/carers' awareness, receipt, and reading of the educational materials. Demographic information such as geographic region and HCP specialty will also be captured (see Annexes 4 and 5). This information is required to further characterise the respondent population, including the number of patients.

The KRM topics for both the HCP and parent/carer surveys are listed in Section 8.3.3:

8.3.2. Question design

The survey will start with screening questions. The surveys will be composed of multiple choice and close-ended questions. There will be no open-ended questions included.

8.3.3. Outcome definitions

This study will assess the proportion of parents/carers and referring HCPs at six months post treatment with Strimvelis that understood the possible risks relating to:

Safety concerns (KRM topics):

- 1. Malignancy due to insertional oncogenesis (e.g. leukaemia, myelodysplasia)
- 2. Autoimmunity
- 3. Unsuccessful response to gene therapy
- 4. Pregnancy

Other areas of interest:

- Requirement for long-term monitoring
- Receipt of the patient treatment alert card

The proportion of parents/carers and referring HCPs who acknowledge receipt of routine and additional risk minimization measures (e.g., SmPC/PIL, educational materials, Patient Alert Card) will be assessed as a measure of implementation.

The type of medical specialty and experience of referring HCPs will be summarized.

The primary outcome of these surveys is the proportion of parents/caregivers and referring HCPs that provide correct responses to a series of questions concerning the specific risks associated with Strimvelis.

Sufficient understanding of a key risk message can be assumed if at least 80% or more respondents correctly answer all questions that are included within that particular key risk message [ISPE White Paper 2016].

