8.5. Study size

All parents/carers and referring HCPs from patients enrolled in the Strimvelis product registry will be invited to complete the surveys. The study will recruit for approximately two years until 10 referring HCPs and 10 parents/carers have completed their respective surveys (length of study may vary contingent upon product uptake).

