8.7.1. Essential analysis

A frequency distribution of responses to each question (the number of respondents who give an answer to each question) will be presented. Summary statistics will be prepared describing the proportion of parents/carers and referring HCPs for whom questionnaires were returned relative to the total number of parents/carers and referring HCPs of patients eligible for enrolment into the study.

For the analysis population, the proportion of participants answering each question correctly and incorrectly will be summarized. In case of multiple choice questions, the number and proportion of participants reporting each response will be provided.

For the analysis population, the proportion of correct answers to survey questions overall and by risk category will be summarized.

Table shells are presented in Annex 2.

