of the disease (e.g. hepatic steatosis, CNS manifestations, and hearing and neurobehavioural disorders).	c. I don't know			
15. Patients should be followed up indefinitely	a. True			
using routine haematological tests.	b. False			
	c. I don't know			
16. Which tests can be used during follow-up if loss of immunity is suspected?	a. Lymphocyte counts, including T-cell differential counts.			
	b. T-cell function [as measured by T-cell proliferative capacity to mitogen challenge (TCA/PHA)].			
	c. ADA metabolite levels (e.g. dAXP levels).			

Answer	N	% (total)
a. Yes b. No c. I don't know		
a. Yes b. No c. I don't know		
a. Trueb. Falsec. I don't know		
a. True b. False c. I don't know		
	a. Yes b. No c. I don't know a. Yes b. No c. I don't know a. True b. False c. I don't know a. True b. False	a. Yes b. No c. I don't know a. Yes b. No c. I don't know a. True b. False c. I don't know a. True b. False

 Table 4. Summary of HCP survey results

		Correct answer		
No.	Question	Yes	No	N total; %Yes
1	Have you received copies of the following educational materials about Strimvelis for healthcare providers?			
2	Did you read the provided educational materials about Strimvelis?			

		Correct answer		
No.	Question	Yes	No	N total; %Yes
3	Strimvelis is recommended as			, , , , , , , , , , , , , , , , , , , ,
	first-line therapy for any			
	patient affected by ADA-			
	SCID.			
4	Strimvelis is indicated for the			
	treatment of patients with			
	severe combined			
	immunodeficiency due to			
	ADA deficiency, for whom no			
	suitable HLA matched related			
	stem cell donor is available.			
5	Strimvelis is contraindicated in			
	patients with a history of			
	previous gene therapy.			
	provious gene merupy.			
	Total (Q1-5)			
Gene	therapy for ADA-SCID and malign	nancy risk (e.g. leuk	kaemia)	
6	Patients eligible to receive			
	treatment with Strimvelis			
	should have a bone marrow			
	harvest for stem cell back-up at			
	least 3 weeks prior to treatment			
	with Strimvelis.			
7	Parents and carers of patients			
	receiving treatment with Strimvelis should be educated			
	on the fact that the patient			
	should not be able to donate			
	blood, organs, tissues, or cells			
	for transplantation.			
8	It is recommended that patients			
	treated with Strimvelis are			
	regularly followed up			
	clinically (at least annually).			
9	Strimvelis is contraindicated in			
	patients with a current or			
	previous history of leukaemia			
	or myelodysplasia.			

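### Tables 4 and 8 score receipt and reading of the materials as correct answers, so the planned overall proportion correct depends partly on distribution

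*Protocol*

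**What the plan says.** Section 8.3.3 draws a line between two kinds of result. The primary outcome is the proportion of parents/carers and referring HCPs who "provide correct responses to a series of questions concerning the specific risks associated with Strimvelis". Acknowledged receipt of the risk minimisation measures "will be assessed as a measure of implementation". The abstract and section 7 make the same division by placing receipt of the educational materials among additional analyses. Section 8.3.1 likewise mentions awareness, receipt and reading apart from understanding of the key risk messages.

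The only criterion for sufficient understanding, also in section 8.3.3, works per key risk message: it is met if "at least 80% or more respondents correctly answer all questions that are included within that particular key risk message".

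Section 8.7.1 plans that "the proportion of correct answers to survey questions overall and by risk category will be summarized" and refers to the table shells in Annex 2. It excludes no item.

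In Annex 2 (section 14.1), Table 4 has the column heading "Correct answer", split into Yes and No. Its first two rows are "Have you received copies of the following educational materials about Strimvelis for healthcare providers" and "Did you read the provided educational materials about Strimvelis". Both rows are counted in a subtotal over Q1-5 and in the closing total over Q1-20. Table 8, for parents/carers, uses the same heading, starts with the matching two questions and prints a subtotal over Q1-5. It prints no total over all 16 questions. Tables 2 and 6 already report receipt and reading separately for the two surveys.

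**The concern.** Whether a respondent received or read a leaflet has no correct answer and says nothing directly about any risk. Once these two items are scored as correct or incorrect and added to the totals, a percentage presented as correct answers combines knowledge with delivery of the materials. It rises when delivery was good and falls when delivery was poor, at the same level of knowledge.

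The study needs to tell these two failures apart. If materials did not arrive, the remedy lies in distribution. If they arrived and were not understood, it lies in their content. An overall figure that mixes the two blurs that distinction in the final report to the EMA.

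**Working it through.** The protocol states no figure for these totals, so there is none to reproduce. The check asks how far each total can move through Q1 and Q2 alone.

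**Inputs from the documents**
- HCP total (Table 4): 20 items, of which 2 are receipt and reading, so 2/20 = 10%.
- Q1-5 subtotal (Tables 4 and 8): 5 items, of which 2 are receipt and reading, so 2/5 = 40%.
- Parent/carer survey (Table 8): 16 items, of which 2 are receipt and reading, so 2/16 = 12.5%. This assumes that the overall proportion of section 8.7.1 is formed from all 16 items.
- Respondents: recruitment runs "until 10 referring HCPs and 10 parents/carers have completed their respective surveys". Ten HCPs give 10 × 20 = 200 item responses, of which 10 × 2 = 20 come from Q1 and Q2.

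**Assumed quantities**
- d: the proportion scored correct on Q1 and Q2 together, from 0 (nobody received and read the materials) to 1 (everyone did).
- q: the proportion correct on the other items in the total.

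**Formula.** With k items in the total:

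total = (2d + (k − 2)q) / k

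At fixed q, moving d from 0 to 1 changes the total by 2/k.

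**Results at q = 80%**
- HCP Q1-20: (2d + 18 × 0.80)/20. This is 14.4/20 = 72% at d = 0, 15.4/20 = 77% at d = 0.5, and 16.4/20 = 82% at d = 1.
- Q1-5: (2d + 3 × 0.80)/5. This is 2.4/5 = 48% at d = 0 and 4.4/5 = 88% at d = 1. At d = 0 the subtotal cannot exceed 3/5 = 60%, even if Q3-5 are all answered correctly.
- Parent/carer Q1-16, if formed: (2d + 14 × 0.80)/16. This is 11.2/16 = 70% at d = 0 and 13.2/16 = 82.5% at d = 1.

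**Range over other assumed values of q** (from d = 0 to d = 1)

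| q | HCP Q1-20 | Q1-5 | Parent/carer Q1-16 (assumed) |
|---|---|---|---|
| 60% | 54% to 64% | 36% to 76% | 52.5% to 65% |
| 75% | 67.5% to 77.5% | 45% to 85% | 65.6% to 78.1% |
| 80% | 72% to 82% | 48% to 88% | 70% to 82.5% |
| 90% | 81% to 91% | 54% to 94% | 78.8% to 91.3% |

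The widths are 10, 40 and 12.5 points whatever q is.

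**Key risk messages.** Q1 and Q2 stand outside every key-risk block in Tables 3, 4, 7 and 8. The per-message results therefore contain no term in d.

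**After removal of Q1 and Q2.** The totals cover 3 items (Q3-5), 18 items (HCP Q3-20) and, if formed, 14 items (parent/carer Q3-16). Each then equals q.

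**The case against.** The strongest reply is that nothing decisive is touched. The primary outcome is defined on questions about specific risks, so its wording already leaves out Q1 and Q2. The only decision rule works per key risk message, and neither item belongs to one. The overall proportion is one descriptive summary among several, and the protocol does not call it the headline result. All of this stands. A reader might infer that good distribution could carry the study over its 80% line, or that the understanding result follows distribution instead of knowledge. The documents support neither reading. No 80% threshold is set for the overall or Q1-5 totals, and 18 of the 20 HCP items are neither receipt nor reading.

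It can also be said that the full 10-point swing is an extreme case. Section 8.9 says the materials were distributed at registry entry, so d may lie near 1. At q = 80% and d = 1 the HCP total is then 82%, only 2 points too high. This is fair. The swing is a bound, not a forecast.

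The tables print every item, so a reader could take out the two rows. That limits the harm but does not make the printed totals right. Nor is the matter simply left to an analysis plan, because section 8.7.1 refers to these shells and the shells fix what the totals contain.

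The protocol text shown gives no key for scoring Q1 and Q2. HCP Q1 asks for all documents received, and Q2 also allows 'Some' and 'I don't know'. The bounds above hold under any key, since d stays between 0 and 1. The missing key is itself a sign that the items do not fit a correct/incorrect column.

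Finally, some remaining items are also reports of conduct or events: HCP Q10 and Q11, and parent/carer Q7. Totals without Q1 and Q2 would therefore not be pure measures of knowledge. This stands. The fix removes the receipt and reading component and no more.

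**Conclusion.** The point holds as a defect in the composition of the totals. Tables 4 and 8 count two implementation items as correct answers, against the division made in section 8.3.3, and section 8.7.1 does not exclude them from the overall proportion.

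The size is at most 10 points for the HCP total and at most 40 points for the Q1-5 subtotal in either survey. For parents/carers it is at most 12.5 points, conditional on an overall figure from all 16 items, which section 8.7.1 implies but Table 8 does not print. The item counts come from the shells. The values of d and q are assumptions, and only the widths of the ranges are free of them.

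The effect is confined to descriptive totals. The definition of the primary outcome, the four key-risk-message results and their 80% criterion are unaffected, so no conclusion on sufficient understanding can change through this route. It should be corrected because the result is mis-composed as written and the correction is nearly free.

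**What to change.** - Remove Q1 and Q2 from Tables 4 and 8, and report them only in Tables 2 and 6.
- Relabel the subtotal as Q3-5 in both tables and the HCP total as Q3-20. Any parent/carer overall figure should be labelled Q3-16.
- Add one sentence to section 8.7.1 stating that the overall proportion of correct answers excludes the receipt and reading items.

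The cost is an edit to two shells and one sentence, with no new data. The overall figure may come out slightly less favourable where receipt and reading were high: in the worked case at q = 80% and d = 1, the HCP figure would be 80% instead of 82%.

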Variables: Two survey instruments with approximately 20 questions are included in this study, a HCP survey and a parent/carer survey. Survey questions are based on the Strimvelis prescribing information and educational materials, and will evaluate HCPs' and parent/carers' understanding of the key risk messages (KRMs). The questions will also assess HCPs' and parent/carers' awareness, receipt, and reading of the educational materials. Demographic information, including geographic region and HCP specialty, will be collected.

Data sources: Referring HCPs and parents/carers of patients enrolled within the registry will be asked to complete the survey. Surveys will be developed in English and translated in the parent/carers' and HCPs' local language. Survey's will be conducted via telephone interview.

Study size: The study will recruit for approximately two years until 10 referring HCPs and 10 parents/carers have completed their respective surveys (length of study may vary contingent upon product uptake). Results of surveys are distinct for each of the groups and will be reported separately.

Data analysis: Data from all survey respondents will be analysed and reported as descriptive statistics. A frequency distribution of responses to each question will be presented. Summary statistics will be prepared describing the proportion of referring HCPs and parents/carers for whom questionnaires were returned relative to the total number of referring HCPs and parents/carers of patients eligible for enrolment into the study.

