8.6.2. Resourcing needs

This study is overseen by a senior PhD level epidemiologist, MD level physician and GSK Study Accountable Person (SAP). Study management, the reporting analysis plan, data collection, data analysis and reporting will be provided by a CRO.

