8.7. Data analysis

There are two distinct analysis populations comprising all (1) Parents/Carers and (2) referring HCPs recruited in the study. Information on response rate will be summarized. For each analysis population, all data from all survey respondents will be analysed and reported as descriptive statistics. Each survey will be analysed for all countries combined.

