8.9. Limitations of the research methods

This study has the following limitations:

- Small sample size: given the rarity of the disease a high response rate is important. The response rate will most likely be dependent on who is willing to participate in the registry. The actual time of survey participation coincides with the follow up regime of the registry and is thus not seen as a major challenge.
- Recall bias: there may be a potential recall bias when answering more complex questions as the educational materials were distributed at least 6 months prior to the telephone interviews (at the time of entering the registry and consenting to both the registry and this survey). Therefore medical terms are often explained before asking a specific question, to ensure understanding of the topic.
- Possible bias due to telephone interviewer led questioning and their delivery style.
- Possible misunderstanding on the part of participants or questionnaire fatigue could lead to inaccurate answers. Therefore, questions have been limited to approximately 20 only and some of the medical terms or themes are introduced before a particular question is asked.
- The participants' educational attainment is unknown; and we assume that participants are representative of the entire Strimvelis HCPs/parents/carers spectrum and that the questions can be understood across the entire educational range.
- Parents/Carers of patients who did not respond to treatment may understandably be under extreme stress with potentially many medical interactions happening unrelated to Strimvelis which may impact their recall of educational materials. Stratification of the survey results by response to treatment may help in discarding this imbalance.

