8.10. Study closure/uninterpretability of results

The study will be closed when 10 parents/care givers and 10 HCPs have completed the surveys. The survey will begin with a question indicating the agreement to participate in the survey. If the individual does not agree, the survey will be ended.

Ethics approval will be sought as required by individual countries.

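### An observed 80% in 10 respondents is allowed to establish sufficient understanding of a key risk message, with no statement of precision attached to the rule

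*Protocol*

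**What the plan says.** Section 8.3.3 (Outcome definitions) gives the criterion for each KRM: "Sufficient understanding of a key risk message can be assumed if at least 80% or more respondents correctly answer all questions" belonging to it. There are four KRMs (malignancy, autoimmunity, unsuccessful response, pregnancy), each put to two groups.

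Section 8.5 recruits "until 10 referring HCPs and 10 parents/carers have completed their respective surveys", and Section 8.10 adds: "The study will be closed when 10 parents/care givers and 10 HCPs have completed the surveys". The groups are not pooled; the Abstract says: "Results of surveys are distinct for each of the groups and will be reported separately". The criterion is therefore applied to 10 people at a time and is met at 8 of 10.

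Section 8.7 states that "all data from all survey respondents will be analysed and reported as descriptive statistics". Section 8.7.1 specifies that "the proportion of participants answering each question correctly and incorrectly will be summarized", together with the proportion of correct answers overall and by risk category. The table shells in Annex 2 hold counts and percentages.

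Section 8.9 begins its list of limitations with: "Small sample size: given the rarity of the disease a high response rate is important". It goes on to discuss response rate and does not connect the small number to the 80% criterion. The same section assumes that participants represent all Strimvelis HCPs, parents and carers.

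**The concern.** The criterion turns a point estimate from 10 people into a conclusion about understanding. A sample proportion of 80% at this size says little about whether the underlying proportion is above or below 80%, and nothing in the protocol tells the reader so.

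The results go mainly to the EMA (Section 11.1) as evidence on whether risk minimisation has worked, including for insertional oncogenesis. A message understood by 70% or 75% of the target group could be reported as sufficiently understood. One that sits exactly at the benchmark could be reported as falling short. In both cases the wording would suggest a firmness that the data do not have.

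**Working it through.** **Plan's own figure.** The protocol derives the 10 per group from no power or precision calculation, so there is nothing to reproduce. It is a feasibility number in an ultra-rare disease.

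**Inputs.** n = 10 per survey (Sections 8.2, 8.5, 8.10). Criterion: observed all-correct proportion of at least 80% (Section 8.3.3), which is X ≥ 8. Let p be the proportion of the target population who would answer every question of a KRM correctly. *Assumption for steps 1 and 2:* respondents are a random sample from a large population.

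**Step 1: exact 95% intervals.** The Clopper-Pearson lower limit solves P(X ≥ x | p) = 0.025, and the upper limit solves P(X ≤ x | p) = 0.025. For 10/10 the lower limit is 0.025^(1/10) = 0.692.

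| Observed | Exact 95% interval |
|---|---|
| 8/10 | 44.4% to 97.5% |
| 9/10 | 55.5% to 99.7% |
| 10/10 | 69.2% to 100% |

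The choice of method does not change the reading. For 10/10 the lower limit is 72.2% (Wilson), 67.9% (Agresti-Coull), 78.3% (Jeffreys) or 74.1% (one-sided 95% exact). All are below 80%.

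**Step 2: how often the criterion is met.** P(X ≥ 8) = 45p⁸(1−p)² + 10p⁹(1−p) + p¹⁰. At p = 0.7 this is 0.2335 + 0.1211 + 0.0282 = 0.383. At p = 0.8 it is 0.3020 + 0.2684 + 0.1074 = 0.678.

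| True p | Probability that the criterion is met |
|---|---|
| 50% | 5.5% |
| 60% | 16.7% |
| 70% | 38.3% |
| 75% | 52.6% |
| 80% | 67.8% |
| 90% | 93.0% |

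A message at 75% passes slightly more often than not. A message exactly at 80% fails with probability 1 − 0.678 = 32%.

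**Step 3: a small target population.** The protocol does not give the number treated, so a range of population sizes M is assumed. With 10 sampled out of M, take the smallest number K of people with full understanding for which the hypergeometric P(X ≥ x) exceeds 0.025. For example, with M = 20 and x = 10:

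- K = 16 gives C(16,10)/C(20,10) = 8008/184756 = 0.043, which is above 0.025.
- K = 15 gives 3003/184756 = 0.016, which is below it.
- The lowest compatible value is therefore 16/20 = 80%.

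| Assumed M | Lowest compatible with 8/10 | Lowest compatible with 10/10 |
|---|---|---|
| 12 | 67% | 92% |
| 20 | 55% | 80% |
| 30 | 50% | 77% |
| 50 | 48% | 74% |

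With about 20 or fewer people in the target population, 10/10 could exclude values below 80%. The boundary is approximate because the values move in steps of one person. Even at M = 12, 8/10 does not exclude values below 80%.

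**Step 4: can the criterion be read from the planned tables?** Tables 4 and 8 have one row per question and subtotals by topic. Neither has a row for respondents who answered every question of a KRM correctly, which is the quantity Section 8.3.3 needs. The grouping is also unsettled: HCP KRM 1 covers Q9 to Q11 in Table 3 and Annex 4, but the malignancy block of Table 4 runs from Q6 to Q11.

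**The case against.** The strongest reply is that this is a descriptive survey. The ENCePP checklist comments say so, no test or error rate is attached to the 80%, and the figure is a cited benchmark. That is a good reason not to ask for a hypothesis test or a larger study. It does not cover the wording of Section 8.3.3, which moves from a sample proportion to an assumption of sufficient understanding. Section 8.9 then carries that beyond the respondents by assuming they represent everyone concerned.

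A second reply is that everyone linked to a registry patient is invited, the disease is very rare and treatment is currently given at one hospital, so 10 respondents may be a large share of the target population. This stands in part. A reader might infer that no result from 10 respondents can ever exclude understanding below 80%. The documents do not support that flat statement, because the number treated is not given and step 3 shows that it fails in a small enough population.

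A third reply is that intervals may be specified elsewhere. Section 8.6.2 says: "Study management, the reporting analysis plan, data collection, data analysis and reporting will be provided by a CRO". That reporting analysis plan is not at hand, so the absence of intervals from the protocol does not show that none will be reported. The criterion itself is fixed in the protocol, however, and an interval added later would not change what 8 of 10 is allowed to establish.

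Two further inferences go too far:

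- *That the rule often misclassifies.* This is true only near the threshold. At a true 60% the criterion is met 17% of the time, and at 90% it is missed 7% of the time.
- *That four KRMs multiply the chance of a false pass.* Such a calculation needs independence between answers from the same 10 people, which is implausible. It also needs a criterion that any one KRM passes, which the protocol does not have.

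**Conclusion.** The point holds in this form: the protocol fixes a point-estimate criterion at 10 respondents per survey and attaches no statement of precision to it, so the conclusion it permits at 8 of 10 is firmer than the data can support. In a large population, 8/10 is compatible with true understanding of 44% to 97%, and the criterion cannot separate values near 80% (met with probability 38% at 70%, 53% at 75% and 68% at 80%). It does separate values well away from the benchmark.

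The figures assume random sampling from the target population. They narrow as that population shrinks: at about 20 or fewer, 10/10 could exclude values below 80%, while 8/10 would remain compatible with about 55% (population of 20) to 67% (population of 12). The 80% benchmark and the number of respondents are not in dispute.

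**What to change.** Keep 10 respondents per group and the 80% benchmark, and make four changes:

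1. In Section 8.3.3, replace the statement that sufficient understanding can be assumed with: *the 80% benchmark was met / not met in this sample*.
2. Settle which questions belong to each KRM, so that Tables 3 and 4 and Annex 4 agree on HCP KRM 1.
3. Add to Tables 4 and 8 one row per KRM for respondents who answered all its questions correctly, with the exact (Clopper-Pearson) 95% interval.
4. State in Section 8.3.3 or 8.9 that, if respondents are viewed as a sample of a larger population, 10 respondents cannot establish understanding of 80% or more.

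The cost is a few table rows (four per survey), some rewording and a less favourable conclusion. No extra respondents, questions or time are needed.

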Please answer based on your knowledge of Strimvelis as informed by the Strimvelis Educational Materials, including the product Summary of Product Characteristics (Product Label).
3. Strimvelis is recommended as first-line therapy for any patient affected by ADA-SCID.
Please select one response.
a. True
b. False
c. I don't know
4. Strimvelis is indicated for the treatment of patients with severe combined immunodeficiency due to ADA deficiency, for whom no suitable HLA matched related stem cell donor is available.
Please select one response.
a. True
b. False
c. I don't know
5. Strimvelis is contraindicated in patients with a history of previous gene therapy.
Please select one response.
a. True
b. False

c. I don't know

CONFIDENTIAL

WWEpi Project number: PRJ2678/205881

6. Patients eligible to receive treatment with Strimvelis should have a bone marrow harvest for stem cell back-up at least 3 weeks prior to treatment with Strimvelis. Please select one response. a. True b. False c. I don't know 7. Parents and carers of patients receiving treatment with Strimvelis should be educated on the fact that the patient should not be able to donate blood, organs, tissues, or cells for transplantation. Please select one response. a. True b. False c. I don't know 8. It is recommended that patients treated with Strimvelis are regularly followed up clinically (at least annually). Please select one response. a. True b. False c. I don't know 9. Strimvelis is contraindicated in patients with a current or previous history of leukaemia or myelodysplasia. [KRM 1] Please select one response. a. True b. False

c. I don't know

CONFIDENTIAL

WWEpi Project number: PRJ2678/205881

10. Have you given advice to parents/carers/patients regarding monitoring for signs and symptoms of leukaemia? [KRM1] Please select one response. a. Yes b. No c. I don't know 11. Have you performed blood tests (including red blood cell indices, white blood cell count differential, platelet count, and a routine biochemistry screen) within the first year of a patient's returning from treatment with Strimvelis? [KRM1] Please select one response. a. Yes b. No c. I don't know 12. Regular monitoring for clinical autoimmunity (possibly including tests for auto-antibodies) is recommended. [KRM2] Please select one response. a. True b. False c. I don't know 13. Autoimmunity may be observed during immune reconstitution after gene therapy. [KRM2] Please select one response. a. True b. False

b. No

c. I don't know

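### The HCP malignancy message has three items in Annex 4 and Table 3 but six in Table 4, so its result under the 80% all-correct rule can depend on which grouping is followed

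*Protocol*

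**What the plan says.** Section 8.3.3 sets the protocol's only success threshold. Understanding of a message is assumed if "at least 80% or more respondents correctly answer all questions that are included within that particular key risk message". Section 8.5 recruits "until 10 referring HCPs and 10 parents/carers have completed their respective surveys". Section 8.3.3 names four KRM topics but does not say which questions belong to each.

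For the HCP survey, membership of KRM1 (malignancy) has to be read from the annexes:

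- **Annex 4** tags three questions. Q9 reads "Strimvelis is contraindicated in patients with a current or previous history of leukaemia or myelodysplasia. [KRM 1", Q10 reads "Have you given advice to parents/carers/patients regarding monitoring for signs and symptoms of leukaemia? [KRM1", and Q11, on blood tests, ends "within the first year of a patient's returning from treatment with Strimvelis? [KRM1". Q6, Q7 and Q8 carry no tag; Q8, for example, is "It is recommended that patients treated with Strimvelis are regularly followed up clinically (at least annually".
- **Table 3** (Annex 2) places its KRM 1 heading after Q8 and its KRM 2 heading after Q11, which again gives Q9 to Q11.
- **Table 4** (Annex 2), the results summary, closes its general block with a total for Q1-5, starts the malignancy heading before Q6, and closes that block with a total for Q6-11.

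Section 8.7.1 adds that "the proportion of correct answers to survey questions overall and by risk category will be summarized".

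**The concern.** An all-correct rule is defined only once the item list of each message is fixed. For HCP malignancy the protocol gives two lists, one twice as long as the other. The three extra questions concern a back-up bone marrow harvest, donation of blood, organs, tissues or cells, and regular clinical follow-up. None of them mentions leukaemia or carries a KRM label. Under Table 4, errors on those questions could make malignancy appear not understood when every malignancy question was answered correctly. The by-category summary in Section 8.7.1 is affected in the same way. If this is left open, whoever writes the report to the EMA must choose a grouping, possibly after seeing the answers.

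**Working it through.** **Inputs.** Threshold 80%, all items correct (Section 8.3.3). Ten respondents per survey (Section 8.5), so a pass is at least 0.80 × 10 = 8 of 10. Items k = 3 (Annex 4, Table 3) or k = 6 (Table 4). The per-item probability of a correct answer, p, and the within-respondent correlation, ρ, are not in the documents and are assumed over a range. The protocol gives no calculation behind the 10 respondents, so there is no figure of its own to reproduce.

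**Step 1: can the verdict change?** No probability model is needed. Suppose all 10 HCPs answer Q9 to Q11 correctly and three of them miss Q6 only.

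- Three-item grouping: 10/10 all correct, pass.
- Six-item grouping: 7/10 all correct, fail.

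The three items are a subset of the six, so the six-item count can never be the higher one. The verdicts differ exactly when at least 8 respondents have Q9 to Q11 right but fewer than 8 have Q6 to Q11 right.

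**Step 2: how likely is it?** With independent items, a respondent has all k items right with probability p^k, and P(pass) = P(Binomial(10, p^k) ≥ 8). With correlation ρ (beta-binomial), p^k is replaced by B(a+k, b)/B(a, b), where a = p(1−ρ)/ρ and b = (1−p)(1−ρ)/ρ; at ρ = 1 it is simply p.

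| p | ρ | All correct, k = 3 | All correct, k = 6 | P(pass), k = 3 | P(pass), k = 6 |
|---|---|---|---|---|---|
| 0.95 | 0 | 0.857 | 0.735 | 0.839 | 0.481 |
| 0.90 | 0 | 0.729 | 0.531 | 0.464 | 0.081 |
| 0.95 | 0.5 | 0.911 | 0.883 | 0.947 | 0.898 |
| 0.90 | 0.5 | 0.826 | 0.777 | 0.756 | 0.606 |
| 0.90 | 1 | 0.900 | 0.900 | 0.930 | 0.930 |

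Because the sets are nested, the difference between the last two columns is the chance that the two groupings give opposite verdicts. At p = 0.90 it is 0.464 − 0.081 = 0.383 with independence, 0.756 − 0.606 = 0.150 at ρ = 0.5, and 0 at ρ = 1.

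**Step 3: does any planned table show the quantity that the rule uses?** Read with Section 8.7.1, the Table 4 totals pool correct answers over questions. In the Step 1 example the Q6-11 total is 57 of 60, or 95%, while the share of respondents with all six correct is 7 of 10, or 70%. The 80% rule applies to the second figure, and no table shell has a row for it.

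**Step 4: the parent/carer tables.** Table 7 puts Q11 to Q14 under KRM 3 and Q15 and Q16 under KRM 4. In Table 8 the total directly below Q11 to Q14 is labelled Q15-16.

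**The case against.** The strongest reply is that Table 4 never uses the term KRM. Its heading says only malignancy risk, and its columns show correct answers question by question. The two places that do label KRM membership agree on three items, so Table 4 could be read as an untidy shell rather than a rival definition. That has force, and it shows which way to reconcile. It does not remove the conflict: Table 4 is the only HCP shell with totals by risk category, its malignancy total is explicitly Q6-11, and Section 8.3.3 does not say which list governs. A later reporting analysis plan (Section 8.6.2) could settle presentation, but it would inherit two conflicting lists from the protocol.

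A reader might go further and infer that pass or fail depends on the number of items as much as on understanding, since HCP messages range from two to five items under the Table 3 grouping. The documents do not support that. The effect rests on independent, equally difficult items; it shrinks with correlation and vanishes at ρ = 1. Equal difficulty is itself doubtful, because Q10 and Q11 ask what the HCP has done and the others test knowledge. Even with independence, moving p from 0.80 to 0.95 at three items shifts P(pass) from 0.064 to 0.839. Unequal length under a criterion-based rule is a design choice, and no ranking of messages is planned. Section 8.7.1 already reports each question separately, so a long message can be inspected item by item.

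**Conclusion.** The contradiction is real: KRM1 for HCPs has three items in Annex 4 and Table 3 and six in Table 4, and this list feeds the protocol's only success threshold. The malignancy verdict can therefore depend on the grouping. That is a possibility and not a certainty; it needs enough errors on Q6 to Q8 to bring the all-correct count below 8 of 10. The illustrative chance of opposite verdicts at 90% per item runs from 0.38 with independent items to none at full correlation, assuming exactly 10 respondents and equal accuracy across items. Separately, the planned totals do not show the share of respondents with all items correct, and one Table 8 total is mislabelled. Unequal message length is at most a caution when reading the results.

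**What to change.** 1. In Table 4, make malignancy Q9 to Q11, as in Annex 4 and Table 3. Move Q6 to Q8 to the general block, relabel that block's total Q1-8, and relabel the malignancy total Q9-11.
2. In Table 8, relabel the total under unsuccessful response from Q15-16 to Q11-14.
3. In Tables 4 and 8, add one row per KRM with the number and percentage of respondents who answered all its items correctly. This is the figure to compare with 80%.

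The 80% rule stays as it is. The cost is edits to two table shells, with eight added rows in all (four KRMs in each table). No question and no data item changes. The edits should be made before any responses are reviewed.
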